14.2 Sample Size/Accrual Rate

The accrual goal of 50 patients is projected to be enrolled over a total period of 4 years based on the observed rate of accrual during the first two years since the protocol was open to patient entry.

The preoperative protocol regimen will have demonstrated an improvement in efficacy if an R0 resection were achieved in at least 16 of 50 patients. The decision rule is associated with 90% power if preoperative FOLFIRINOX and short-course radiation were able to improve the R0 resection rate to 40%. In contrast, the probability of type 1 error is only 3% if the underlying rate of R0 resection were truly the same as the historical data of 20%. All protocol patients who begin the preoperative regimen will be included in the denominator for analysis of the R0 resection rate, including those who do not undergo surgery due to progression or other reasons.

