2.2.3 Neoadjuvant photon chemoradiation in borderline resectable pancreatic adenocarcinoma

In addition to the rationale presented above for the potential benefit of neoadjuvant treatment in resectable pancreatic cancer, patients who present with borderline resectable disease have the added need for both upfront local control and timely systemic therapy. Local control aims to provide potential tumor downstaging to increase the chance of R0 resection. Systemic therapy aims to sterilize micrometastatic disease, as this population is at higher risk for micrometastatic extension at presentation (as high as 80%).¹¹

The largest case series of neoadjuvant therapy in borderline resectable disease comes from MD Anderson.²² One hundred sixty patients with borderline resectable disease (classified due to tumor abutment of the visceral arteries or short-segment occlusion of the SMV) were followed. Of these, 125 (78%) completed preoperative therapy and restaging. Preoperative therapy was generally administered off-protocol, but some patients were treated on protocols designed for patients with locally advanced disease. Chemoradiotherapy consisted of external beam radiation therapy (50.4Gy in 28 fractions or or 30 Gy in 10 fractions) with concomitant chemotherapy with 5-fluorouracil, paclitaxel, gemcitabine, or capecitabine at radiosensitizing doses. Systemic chemotherapy consisted of gemcitabine alone or in combination; some patients received targeted agents. In total, 82 patients had induction chemotherapy and 117 had chemoradiotherapy. After neoadjuvant therapy, 66 (41%) subsequently underwent pancreatectomy. Vascular resection was required in 18 (27%) of 66 patients, and 62 (94%) underwent a margin-negative pancreatectomy. A partial pathologic response to induction therapy (< 50% viable tumor) was seen in 37 (56%) of 66 patients. Median survival was 40 months for the 66 patients who completed all therapy and 13 months for the 94 patients who did not undergo pancreatectomy ($p < 0.001$).

A smaller, retrospective review of patients with borderline resectable pancreatic cancer treated with preoperative chemoradiation and chemotherapy at Fox Chase Cancer Center included 13 patients treated in the neoadjuvant setting with chemoradiation (radiosensitizer fluorouracil (5-FU) in 3 patients, gemcitabine in 9 patients, and capecitabine and bevacizumab in

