1 patient administered with 50.4 Gy in 1.8-Gy fractions.²³ Patients received a median of 3 cycles of full-dose chemotherapy consisting of gemcitabine for 4 patients, gemcitabine and oxaliplatin for 3 patients, gemcitabine and erlotinib for 4 patients, gemcitabine and bevacizumab for 1 patient, and 5-FU and erlotinib for 1 patient. After neoadjuvant therapy, 12 of 13 patients subsequently had surgery, resulting in 2 R1 and 11 R0 resections. Nine patients were alive with a median follow-up of 20 months. Five patients recurred at a median of 4 months.

Finally, a recent series of 170 patients at University of Virginia included 40 patients with borderline resectable disease, and explored the benefit of shorter course radiation in the borderline setting.²⁴ Of the 40 borderline resectable patients enrolled, 34 (85%) completed neoadjuvant therapy consisting of 50 Gy of radiation in 28 fractions in 6 weeks (8 patients) or 50 Gy in 20 fractions in 4 weeks plus chronomodulated capecitabine (8 patients.) After restaging, pancreatic resection was completed in 16 patients (46%). An R0 resection was achieved in 12 of the 16 patients (75%). Notably, 5 patients (63%) treated in 20 fractions had >90% pathologic response versus 1 (13%) treated in 28 fractions ($P < .05$). Borderline resectable patients completing surgery had similar survival to patients with resectable disease who underwent surgery. Patients receiving accelerated fractionation radiation had improved survival compared with patients treated with standard fractionation protocol.

These case series demonstrate early promise for the neoadjuvant approach in pathologic downstaging to R0 resection. The Consensus statement for combined modality treatment of resectable and borderline resectable pancreas cancer states that at the present time, borderline resectable patients should ideally be enrolled in a clinical trial, and in its absence, “induction systemic chemotherapy followed by chemoradiation and CT assessment of resectability is the preferred approach.”¹¹

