14 STATISTICAL CONSIDERATIONS

14.1 Study Design/Endpoints

This is a single-arm, phase II study to investigate the preoperative administration of FOLFIRINOX chemotherapy and accelerated short-course radiation therapy in patients with borderline-resectable adenocarcinoma of the pancreas.

The primary endpoint of this study is R0 resection rate determined by final pathology of the surgical specimen. The previously studied approach involved four months of induction gemcitabine followed by six weeks of neoadjuvant 5-FU-based chemoradiation (50.4 Gy). Our internal data support a historical R0 resection rate of 20% for patients with resectable

disease who received induction chemoradiation (CRT) (8 of 40) or induction chemotherapy followed by chemoradiation (C-CRT) (6 of 30). In a retrospective surgical series at MGH, median tumor size was 29 mm for the CRT group and 35 mm for C-CRT group. Among patients considered 'borderline resectable' upfront (n = 24), 5 of 24 = 21% had eventual margin-negative resection (or 7 of 24 = 29%, if < 1 mm is considered as a negative margin / R0 resection).

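### The 3% type I error for the 16-of-50 rule holds only at a 20% null labelled 'resectable'; on the institution's own borderline patients it is 4% or 38%, depending on an R0 margin rule the plan never states

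*Combined protocol and SAP*

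**What the plan says.** Section 14.2 (Sample Size/Accrual Rate) makes the primary claim depend on one count: "The preoperative protocol regimen will have demonstrated an improvement in efficacy if an R0 resection were achieved in at least 16 of 50 patients". It gives 90% power if the true R0 rate is 40%, and adds that "the probability of type 1 error is only 3% if the underlying rate of R0 resection were truly the same" as the historical 20%. Every patient who begins the preoperative regimen is in the denominator.

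Section 14.1 (Study Design/Endpoints) supplies the 20%: "Our internal data support a historical R0 resection rate of 20% for patients with resectable" disease, from 8 of 40 patients given chemoradiation and 6 of 30 given chemotherapy and then chemoradiation. The same paragraph reports 24 institutional patients considered borderline resectable at the outset. Of these, 5 (21%) had a margin-negative resection, or "7 of 24 = 29%, if < 1 mm is considered as a negative margin / R0 resection".

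The endpoint is R0 as determined by final pathology. Section 5.2.7.2 (Pathology) has margin status recorded and section 10.1.2 (Pathological Response) describes the specimen review. Neither gives a margin distance, and nor does 14.1.

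**The concern.** The null and the trial population carry different disease labels. Sections 1.1, 3.1.4 and 14.1 all describe a borderline-resectable trial, while the 20% is assigned to resectable disease.

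The more consequential gap is the margin rule. Section 14.1 itself shows that the institution's borderline rate moves from 21% to 29% according to whether a clearance under 1 mm counts as negative. If the trial's specimens are read by the looser rule and judged against a null of about 20%, part of any apparent gain comes from the definition and not from the regimen. A single-arm trial has no concurrent control to reveal this. At stake is whether 16 R0 resections in 50 patients supports an unqualified statement that efficacy has improved.

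**Working it through.** **Inputs.** n = 50, cut-off 16 and target 40% (14.2). Null counts 8/40 and 6/30; borderline counts 5/24 and 7/24 (14.1).

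**Null.** (8 + 6)/(40 + 30) = 14/70 = 20%.

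**Formula.** The chance of meeting the rule at true rate p is the exact binomial tail P(X ≥ 16) = Σ C(50, k) p^k (1 − p)^(50 − k), summed over k = 16 to 50.

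**The plan's own figures.** At p = 0.20 the tail is 0.0308, and at p = 0.40 it is 0.9045. The stated 3% and 90% reproduce.

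**The same rule at the institution's borderline rates** (unrounded fractions):

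| True rate with no improvement | P(16 or more of 50) |
|---|---|
| 14/70 = 20.0% | 3.1% |
| 5/24 = 20.8% (under 1 mm not counted as R0) | 4.3% |
| 7/24 = 29.2% (under 1 mm counted as R0) | 38.0% |

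**Smallest cut-off with error of at most 5% at n = 50, and its power at 40%:**

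| Null | Cut-off | Type I error | Power at 40% |
|---|---|---|---|
| 5/24 | 16 | 4.3% | 90% |
| 7/24 | 21 | 3.6% | 44% |

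Moving to the stricter borderline null therefore changes neither the cut-off nor the power. Moving to the looser one changes both.

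**Interval at the threshold.** 16/50 = 32%. The exact (Clopper-Pearson) 90% limits are the 5th percentile of Beta(16, 35) and the 95th percentile of Beta(17, 34), which are 21.2% and 44.5%. The interval excludes 20% and 5/24 = 20.8%, the latter narrowly. It contains 7/24 = 29.2%.

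**Precision of the borderline rates.** Exact 95% intervals are 7% to 42% for 5/24 and 13% to 51% for 7/24.

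**The case against.** The strongest defence is that the plan makes no calculation error and that its null has borderline support. Section 14.2 states the 3% conditionally on 20%, and it is correct there. The stricter borderline figure, 21%, stands in the same paragraph and raises the error only to 4.3%. An institutional historical control is a defensible choice for phase II. All of this stands, so the population label alone does little harm.

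Three stronger readings are tempting, and the documents do not support them.

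- A reader might infer that the 3% is wrong. It is right for the null named; what is unsettled is whether that null fits the endpoint.
- A reader might infer that the label shows a lenient benchmark. Resectable disease would ordinarily have the higher R0 rate, so the label taken literally does not flatter the trial. It may be a slip. Section 2.2.5 reports positive margins in 4 of 21 resected patients in the institution's study of resectable disease, so 17 of 27 analysed (63%) were margin-negative, which is hard to square with 20%. The documents do not settle it.
- A reader might take the outside borderline series in section 2.2.3 as the true null. In the largest, "62 (94%) underwent a margin-negative pancreatectomy", a percentage of the 66 resected; over the whole cohort it is 62/160 = 38.75%. The 40-patient series gives 12/40 = 30%. At those rates the rule is met with probability 87% and 43%. But these are derived rates from other regimens. The larger series was treated mostly off-protocol and under a different case definition, and neither summary states a margin rule. The resection percentage printed for the 40-patient series (46%, for 16 patients) matches neither 16/40 = 40% nor 16/34 = 47%. A third series reports 11 R0 of 13, but lists 13 resections among 12 operated patients. These series are context, not a replacement null.

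**Conclusion.** The concern holds, with limits. The rule's false-positive probability is 3.1% at the stated 20%, 4.3% at the institution's stricter borderline rate and 38% at its looser one. The plan leaves open which of the last two applies because it does not define R0 by margin distance. Under the stricter rule the design survives intact and only the stated error and the wording need changing. Under the looser rule, 16 of 50 would not show improvement over the institution's own borderline patients.

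The 4.3% and 38% treat 5/24 and 7/24 as the true rates without improvement. With 24 patients both are imprecise, so these figures show how sensitive the claim is to the margin rule and are not settled error rates. The conclusion does not depend on the outside series.

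**What to change.** In 14.1 and 14.2, keeping n = 50:

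1. Correct or explain the resectable label on the 14/70 figure.
2. State the margin rule that defines R0, and take the null from the borderline series under that same rule.
3. If the stricter rule is adopted, keep the cut-off of 16 and restate the type I error as about 4% at 5/24 (21%).
4. State that under the looser rule the same cut-off carries 38% error. An error of 5% or less would need at least 21 of 50, with power of about 44% at 40%, so 16 of 50 could not then be called an improvement.
5. Word success as exceeding the named institutional historical rate, and report the observed rate with its exact 90% interval (21% to 44% if the result is 16 of 50).
6. Cite the outside series (30%, 39%, and 11 of 13) as context only, saying that regimens, case definitions and margin rules differ or are not stated.

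The cost is text and no extra patients. The downside is a less favourable stated error and a narrower claim.

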14.3 Stratification Factors

Not applicable.

14.4 Analysis of Secondary Endpoints

Progression-free survival: All patients who start the protocol therapy will be analyzed based on the definition in Section 10.1.3. The Kaplan-Meier method will be used to estimate progression-free survival with 90% confidence intervals constructed by Greenwood's formula.

Overall survival: Overall survival will be defined as the duration between the dates of protocol enrollment and death. The survival time of patients who are not known to have died will be censored at the date they were last known to be alive.

Toxicity: All patients who begin protocol treatment will be included in the toxicity profile. Toxicity summaries will include the frequency and proportion of patients experiencing each type of toxicity, as well as summaries by toxicity category and grade.

Surgical morbidity: Analysis will be based on the patients who undergo pancreaticoduodenectomy or distal pancreatectomy. The surgical morbidity rate will be calculated as the proportion of patients who experience peri- and post-operative complications within 30 days of surgery. A 90% confidence interval will be obtained using the exact binomial distribution.

30-day post-operative mortality rate: Analysis will be based on the patients who undergo pancreaticoduodenectomy or distal pancreatectomy. The 30-day post-operative mortality rate will be calculated as the number of patients who die within 30 days of surgery. A 90% confidence interval will be obtained using the exact binomial distribution.

Pathologic downstaging: Analysis will be based on the patients who undergo pancreaticoduodenectomy or distal pancreatectomy. The pathologic downstaging rate will be calculated as the proportion of patients with the primary tumor and nodes downstaged based on final pathology of the surgical specimen.

Local control rate: Local control will be defined as the time from protocol enrollment to the first objective documentation of local failure. Patients who have not experienced a local failure will be censored at the last date they were known to have local control. Kaplan-Meier methodology will be used to estimate the local control rate.

Mutational analysis: The frequency of genetic mutations characterized by the SNaPshot platform (sections 2.6.1 and 8.1) will be summarized. A sample size of 50 patients will provide 90% confidence intervals of maximal width $\pm 12\%$, but the interval widths will be narrower in practice as the mutation rates are typically quite low. We shall analyze PFS differences by mutational status if 5 failure events have been observed within each mutational subgroup. However, the analysis will be purely exploratory due to the limited numbers expected per mutation subgroup.

Circulating biomarkers: The association between plasma SDF1 α and circulating myeloid cells with outcome measures will be examined by logistic regression for ORR or by Cox regression for TTP and OS. Pretreatment levels as well as the changes during and after treatment from baseline will be analyzed. Biomarker levels are typically log-transformed

for analysis, but we shall also consider other approaches such as categorizing based on the observed distribution or dichotomizing at the median.

Patient-reported outcomes: We will use descriptive statistics to describe QOL (EORTC QLQ-C30), symptom burden (ESAS-r) and mood (HADS) for the entire study cohort. Mean values and standard deviations will be used to describe QOL and symptom burden (T-test or Wilcoxon as appropriate). We will score the HADS subscales for depressive and anxiety symptoms categorically, using a cut-off of >7 to describe the proportion of patients with these symptoms. We will use Chi-square or Fisher's Exact Test, as appropriate, to analyze the categorical variables.

Health care utilization: We will use descriptive statistics to describe hospitalizations, ICU stays, ED visits and palliative care use for the entire study cohort. Mean values and standard deviations will be used to describe continuous variables (T-test and Wilcoxon rank sum, as appropriate). We will use Chi-square or Fisher's Exact Test, as appropriate, to analyze the categorical variables.

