10 MEASUREMENT OF EFFECT

10.1 Evaluation Of Response

10.1.1 Imaging Response

Response to therapy and/or progression after induction chemotherapy with FOLFIRINOX will be evaluated in this study using the international criteria proposed by the RECIST (Response Evaluation Criteria in Solid Tumors) committee. Changes in only the largest diameter (unidimensional measurement) of the tumor lesions are used in the RECIST criteria. In the event that CT staging cannot be utilized, restaging MRI will be the substitute modality.

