10.3 Disease Parameters

10.3.1 Measurable disease. Measurable disease is the presence of at least one (1) lesion that can be accurately measured in at least one dimension with longest diameter ≥ 20 millimeters (mm) using conventional techniques (CT, MRI, x-ray) or ≥ 10 mm with spiral CT scan. Measurable lesions must be at least 2 times the slice thickness in mm. All tumor measurements must be recorded in millimeters (or decimal fractions of centimeters).

10.3.2 Target lesions: The primary tumor is the target lesion.

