10.5 Response Criteria

10.5.1 Evaluation of Target Lesions

10.5.1.1 Complete Response (CR): Disappearance of all target lesion.

10.5.1.2 Partial Response (PR): At least a 30% decrease in the sum of the longest diameter (LD) of target lesion, taking as reference the baseline sum LD.

10.5.1.3 Progressive Disease (PD): At least a 20% increase in the sum of the longest diameter (LD) of target lesion, taking as reference the smallest sum LD recorded since the treatment started or the appearance of one or more new lesions (new lesions must be > slice thickness).

10.5.1.4 Stable Disease (SD): Neither sufficient shrinkage to qualify for PR nor sufficient increase to qualify for PD, taking as reference the smallest sum LD since the treatment started.

10.5.1.5 Unknown (UN): Assessment of target lesions cannot be made due to insufficient or unevaluable data. In this case, a concise explanation must be given.

Note: If tumor response data is missing for target lesions, the overall assessment must be UN unless there is new disease that would result in an overall assessment of PD. However, if there is missing or unevaluable data for non-target lesions, but data is available for all target lesions, the overall response for that time point will be assigned based on the sum LD of all target lesions. Additionally, the assessment of CR cannot be made if there is missing or unevaluable data for non-target lesions. In this case, the overall assessment would be PR.

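### The plan relates circulating biomarkers to tumour response only through yes/no ORR; adding an analysis of percent change in the recorded diameter would recover information if the association is roughly linear

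*Combined protocol and SAP*

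**What the plan says.** The circulating-biomarker paragraph of Section 14.4 states that the association with outcome "will be examined by logistic regression for ORR or by Cox regression for TTP and OS". It covers pretreatment levels and changes from baseline. It allows several codings of the biomarker (log-transformed, categorised, split at the median) but one coding of response.

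Section 10 shows what response consists of here:

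- Section 10.3.2: "The primary tumor is the target lesion". The sum of diameters is therefore a single diameter.
- Section 10.1.1: "Changes in only the largest diameter (unidimensional measurement) of the tumor lesions are used in the RECIST criteria".
- Section 10.5.1.2, partial response: "At least a 30% decrease in the sum of the longest diameter (LD) of target lesion, taking as reference the baseline sum LD".
- Section 10.3.1: "All tumor measurements must be recorded in millimeters".

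Section 12.1.2 requires a Tumor Measurement/Staging Form at registration and after each restaging. The calendar in Section 9 places two restaging scans during FOLFIRINOX, one in cycle 4 and one in the last cycle. No analysis of percent change in diameter is planned.

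**The concern.** The cut treats unlike patients as alike. A 29% shrinkage and a 19% growth both count as non-response, and a 31% shrinkage counts the same as complete disappearance. Response criteria need such a cut to assign a category, but nothing in the plan requires a biomarker association to be tested on the category alone.

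The sample is small. Section 14.2 gives "The accrual goal of 50 patients", which is an upper bound here, because the blood draws are optional (Section 9, note 5) and response has its own evaluability rule (Section 10.2.2). At the 31% partial response rate that Section 2.2.4 quotes for FOLFIRINOX, 50 patients give 0.31 × 50 = 15.5 responders. A real association with shrinkage could be missed although the measurements needed to see it are on file.

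**Working it through.** **The plan's own figure.** The only sizing in the plan is for R0 resection: at least 16 of 50, 20% against 40%. The exact binomial distribution gives type I error 3.1% and power 90.4%, matching the stated 3% and 90%. No test level, effect size, expected response rate or power is given for the biomarker analysis.

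**Inputs.**

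- n = 50 (Section 14.2), with 40 as a sensitivity value.
- Response rate 31% from Section 2.2.4. That figure comes from metastatic disease, so 20 to 45% is assumed as a range.
- Two-sided 5% test and correlation r between log biomarker and shrinkage of 0.2 to 0.6: assumed.
- Joint normal distribution with a linear relation; response means shrinkage beyond the cut that yields the assumed rate.

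**Efficiency of the cut.** For a weak to moderate association, the information kept by a yes/no split, relative to the measured scale, is φ(c)² / [p(1−p)], where p is the response rate, c the normal cut point for p and φ the normal density.

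- p = 0.20: 0.280² / 0.16 = 0.49
- p = 0.31: 0.353² / 0.214 = 0.58
- p = 0.40: 0.386² / 0.24 = 0.62

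Under this model, 50 patients analysed as yes/no carry about the information of 25 to 31 analysed on the measured scale (50 × 0.49 to 50 × 0.62).

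**Power by simulation** (20,000 runs per cell, n = 50; linear regression on percent change against the logistic likelihood-ratio test):

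| Response rate | r | Linear | Logistic | Difference (points) |
|---|---|---|---|---|
| 20% | 0.3 | 57% | 33% | 24 |
| 20% | 0.4 | 84% | 54% | 30 |
| 20% | 0.5 | 97% | 74% | 22 |
| 31% | 0.3 | 58% | 38% | 19 |
| 31% | 0.4 | 84% | 61% | 22 |
| 31% | 0.5 | 97% | 82% | 15 |
| 40% | 0.3 | 57% | 41% | 16 |
| 40% | 0.4 | 84% | 64% | 20 |
| 40% | 0.5 | 97% | 85% | 11 |

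Differences are taken before rounding. A smaller simulation (1,500 runs) at a 45% response rate gave differences of 11 to 17 points. With 40 patients and response rates of 20 to 40%, the range is 14 to 29 points. Outside the assumed correlations the difference shrinks: 8 to 11 points at r = 0.2, where both powers are low, and 3 to 10 points at r = 0.6, where both are high. A rank test without any worst-rank group gains less than linear regression: 13, 19 and 13 points at a 31% response rate for r = 0.3, 0.4 and 0.5.

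**A form that favours ORR.** Suppose the biomarker differs only between responders and non-responders, with correlation 0.4 with response itself. At p = 0.31, its correlation with the continuous change is then 0.4 × √0.58 = 0.30. Simulated power is 85% for logistic, 58% for linear and 59% for rank.

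**A worst-rank group.** New lesions and early deaths are not captured by the diameter. Suppose such patients take the worst rank, and these events are unrelated to both the biomarker and the primary tumour's shrinkage (n = 50, overall response 31%, r = 0.4, 3,000 runs):

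| At worst rank | Rank | Logistic | Difference (points) |
|---|---|---|---|
| 5% | 69% | 58% | +11 |
| 10% | 59% | 56% | +3 |
| 15% | 50% | 52% | −2 |
| 20% | 41% | 50% | −9 |

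A separate simulation of the same unrelated case put the difference at about +8 to +10 points with 5% at worst rank, falling to −6 to −12 with 20%. If the events correlate 0.2 with the biomarker, it was about +13 to +16, falling to between −1 and +8. Overall, the worst-rank version runs from about +16 to −12 points.

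**The case against.** The strongest case for leaving the plan alone has four parts.

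*The plan already looks beyond response.* TTP and OS go to Cox regression, and they bear directly on resistance to treatment, the stated interest in Section 8.1. This stands: only the tumour-response question rests on ORR alone.

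*The analysis is exploratory and claims no power.* Circulating biomarkers are not among the objectives in Section 1.3. The plan has several sampling times and codings, with no test level or effect size. This stands, and it keeps the point minor. An exploratory analysis still aims to find signals, however, and the measurements are already collected.

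*ORR handles patients that a diameter cannot.* New lesions count as progression whatever happens to the primary tumour, and Section 10.2.2 keeps patients who progress or die before the end of induction as evaluable. With the micrometastatic risk described in Section 2.2.3, such patients may not be few. This stands. A reader might infer that ORR should give way to a worst-rank analysis as the main result. The worst-rank figures do not support that, because the change in power can be negative.

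*The gain depends on the assumed form.* A linear normal relation favours the continuous outcome by construction, and nothing in the documents establishes linearity or a correlation of 0.3 to 0.5. This also stands. A reader might infer that the plan simply forfeits 11 to 30 points of power. The documents support only the conditional statement.

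**Conclusion.** The point holds as a low-cost improvement, not as an error. Logistic regression on ORR is valid and agrees with the response definition in Section 10; no bias or contradiction is shown. It is, however, the only planned link between the circulating biomarkers and tumour response, and it uses a cut of a single measurement that is already recorded.

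If the association with shrinkage is roughly linear, with r from 0.3 to 0.5, a response rate of 20 to 45%, a two-sided 5% test and 50 patients, regression on percent change has about 11 to 30 points more power. That figure belongs to linear regression on percent change with every patient measured. It does not carry over to a worst-rank analysis, or to a biomarker that separates only responders from non-responders. Because the form of the association is unknown, the two analyses complement each other.

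**What to change.** In the circulating-biomarker paragraph of Section 14.4, before the biomarker data are analysed:

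1. Keep the logistic regression on ORR and the Cox regressions as planned.
2. Add a regression on percent change in the primary tumour's longest diameter from baseline to one named restaging scan, for example the last scan during FOLFIRINOX. Two scans are scheduled, so the choice must be written down. Include every patient with both measurements, including those with new lesions whose primary tumour was measured.
3. Report as a sensitivity analysis a rank version in which patients with new lesions, or who progress or die before restaging, take the worst rank. State that its gain over logistic regression is uncertain.
4. Report how many patients lack a restaging measurement, and why.

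The cost is a few sentences and no new data collection. The downsides are one more exploratory analysis in a set that already has several, and the absence of patients without a restaging measurement from the percent-change model. The retained ORR analysis and the rank version partly cover the latter.
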